As a necessary first step in assessing state-sensitive impulsivity as a causal risk factor for suicidality, this study will assess the short-term effect of tDCS on impulsivity. That is, the researchers will evaluate the potential for tDCS to the right inferior frontal gyrus (rIFG) and left orbitofrontal cortex (IOFC) to modulate behavioral and cognitive impulsivity, respectively, in adolescent suicide attempters. Adolescents in a psychiatric hospital program will be enrolled if they attempted suicide prior to their admission and who had made an impulsive attempt as measured on the C-SSRS (attempt initiated within a day of thinking of it). Participants will be randomized to receive either anodal tDCS to the rIFG, anodal tDCS to the IOFC. Randomization will occur through a computer program (like flipping a coin with participants having an equal chance of being in each group). This will occur after we determine if the participant is eligible for the study. There will be 20 participants in each group. Participants will not be told which group they are randomized into. Baseline impulsivity measures will be re-given after tDCS or sham stimulation to assess changes in impulsivity. Additionally, EEG/ERP data will be collected during the impulsivity tasks, and resting-state EEG data will be collected pre- and post-tDCS.

Participants Adolescents (N = 60) between the ages of 13 and 17 who have been admitted to an adolescent psychiatric hospital (inpatient or partial). Adolescents will be eligible to participate if they: (i) have attempted suicide prior to admission; (ii) had made an impulsive attempt as measured on the C-SSRS (attempt initiated within an hour of thinking of it); (iii) speak and read English fluently, (iv) have no significant cognitive disability based on a standard psychiatric exam, and (v) are not actively psychotic.

Exclusion criteria are: (i) a significant general medical or neurological condition; (ii) history of seizure, head injury, brain surgery or tumor; (iii) intracranial metallic implants or implanted electrical devices; (iv) substance abuse or dependence in the past six months.

Sample Availability. Hospital admission data suggests more than 60 adolescents would meet these study criteria over the two year recruitment period. We have found in other studies recruiting from this site to allow for adequate time for in-depth assessment batteries larger than that of the proposed study.

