After completing these assessments, participants will be randomly assigned to receive either anodal tDCS to rIFG, anodal tDCS to IOFC, or sham stimulation. tDCS at a constant current of 1.5 mA and sham stimulation will be applied for one 20-minute session. In the sham condition, the current will be ramped up to 1.5mA for 30 seconds and then ramped back down to 0. As this commonly used sham procedure produces a brief tingling sensation, participants are kept unaware of their experimental condition. Prior to and tDCS, participants will complete the SST and TCIP, while EEG is recorded to extract ERPs in a single-blind procedure. The participants and PI [name] will be blind to experimental condition, but Co-I [name] will not be blinded. Resting-state EEG, for 5 minutes, will be recorded before pre-stimulation tasks and after post-stimulation tasks. These tasks were specifically chosen because they can be administered well within an hour, the approximate duration of effect from a single-session of tDCS. The side effects questionnaire will be administered following the tDCS session. Ordering of tasks will be counterbalanced. These assessments will take about 3.5 hours total and they will be audio recorded for supervision and training purposes with participants' permission. They will take place in an interview room in the hospital, outside of any clinical care. Adolescent participants and parents will be paid \$100 and \$25, respectively, upon completion of the study.

Assessment Measures.

i. Self-report measures

Wechsler Abbreviated Scale of Intelligence (WASI; Wechsler, 1999): The WASI uses vocabulary, similarities, block design, and matrix reasoning subtests similar to those of the WAIS to provide an estimate of full scale IQ in approximately 30 minutes.

Depressive symptoms will be assessed using the pediatric version of the PROMIS depression scale. Higher scores reflect greater symptom severity.

The Conners-3 Self-Report (Conners-3 SR; Kollins, Epstein, & Conners, 2004): Current ADHD symptoms will be assessed with the Conners-3, with higher scores reflecting greater severity. ADHD will be a covariate in all analyses, as impulsivity is a hallmark of this disorder.

Suicidal ideation will be measured using the Passive and Active Suicidal Ideation Scale (PASIS). Higher scores reflect greater severity of ideation.

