Suicide Intent Scale (SIS): The SIS is an interviewer rating scale that assesses the degree of suicidal intent of a suicide attempt. Higher scores reflect greater suicidal intent.

Screening questionnaire: The screening questionnaire was adapted from those used in other tDCS studies conducted by Co-I [name]. This questionnaire is meant to check for potential head trauma and metallic implants.

Side effects questionnaire: The side effects questionnaire was adapted from those used in other tDCS studies conducted by Co-I [name]. This questionnaire is meant to check for any adverse events from the tDCS stimulation.

Lastly, participants will be asked to report their current medication use, and the information they provide will be confirmed with a parent.

ii. ***Semi-structured interview assessments***

Schedule for Affective Disorders and Schizophrenia for School Aged Children - Present and Lifetime Versions (K-SADS-PL; Kaufman et al., 1997): The K-SADS-PL is a semi-structured diagnostic interview which provides a reliable and valid assessment of DSM-IV psychopathology in children and adolescents. Probes and objective criteria are provided to rate individual symptoms. Inter-rater agreement is high (range: 93% to 100%). Test-retest reliability and kappa coefficients are in the excellent range for present and lifetime diagnoses. Modules selected on the basis of relevance to suicide risk will be administered. These include depressive disorders, mania, psychosis, anxiety disorders, eating disorders, conduct disorder, alcohol and substance abuse, and post-traumatic stress disorder.

Columbia-Suicide Severity Rating Scale (C-SSRS; Posner et al., 2011): The C-SSRS is an interviewer-rating scale, will be used to assess the occurrence of suicide attempts, and to differentiate suicide attempts from interrupted attempts and aborted attempts. To differentiate suicide attempts from nonsuicidal suicidal self-injury, the

former will be defined as any “self-destructive behavior with at least implied intent to die.”

iii. **Computerized neurological tasks – DDT (TCIP), SST**

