This study does not pose greater than minimal risk. Risks associated with participating in this study include some emotional discomfort that may be elicited by discussing sensitive matters such as suicidal thoughts and instances in which the child has tried to harm him- or herself. The child may refuse to answer any questions that lead to too much discomfort. If he or she expresses suicidal thoughts, we will notify the child's doctors so that they can take appropriate precautions. During the interviews and assessments, and when the child is completing the computer tasks he or she may become bored or tired. We will offer breaks frequently, and the child will be told that he or she can quit at any time if he or she gets tired.

Additionally, there is minimal risk in participating in EEG testing or tDCS, as both of these procedures have been demonstrated to be safe for adolescents. tDCS has also been shown to be safe in adults. It has been studied less among children, but studies that have been done so far demonstrate it to be safe for this age group (Andrade et al., 2014; Kessler et al., 2013; Krishnan

et al., 2015; Moliadze et al., 2015). In particular, stimulations at 1.5mA (which will be used in the current study) have been found to be safe and well tolerated in pediatric samples (Kessler et al., 2013). In a recent safety study of tDCS conducted by Poreisz and colleagues (2007) the most common effects were mild tingling sensations (75%), light itching sensation (30%), moderate fatigue (35%), and transient mild headache (11.8%); and most of these effects did not differ from those of placebo stimulation. For the current study, the participant will be asked to report any discomfort immediately. If the participant reports discomfort, the stimulation can be turned off immediately. Participants' parents will be encouraged to bring acetaminophen or ibuprofen in the case of a headache. These medications have promptly resolved discomfort in all prior cases of headaches or neck ache induced by tDCS. EEG is a safe and painless technique that is routinely used in clinical medicine. Lastly, all equipment has been tested by biomedical engineers at Neuroelectrics, who have certified their safety.

Protection against Risk

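### Only a post-stimulation side effects form is described: with no pre-stimulation rating, a participant's fatigue or headache cannot be classed as new, and the form's place in the visit is not stated

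*Combined protocol and SAP*

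**What the plan says.** The combined protocol and SAP sets the timing in the paragraph on the stimulation session, just before Assessment Measures: "The side effects questionnaire will be administered following the tDCS session". The description of the form under Assessment Measures gives its purpose: "This questionnaire is meant to check for any adverse events from the tDCS stimulation". The items are not shown. No pre-stimulation or repeat administration appears in the available text. The SST, the TCIP and resting EEG, by contrast, are all taken before and after stimulation.

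The same paragraph gives the length of the visit ("These assessments will take about 3.5 hours total") and the control: "participants will be randomly assigned to receive either anodal tDCS to rIFG, anodal tDCS to IOFC, or sham stimulation". Apart from the stimulation, no procedure is described as differing by arm. The overview gives the arm size ("There will be 20 participants in each group"), which with N = 60 means three arms.

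Potential Risk names tiredness as an effect of the assessments themselves ("when the child is completing the computer tasks he or she may become bored or tired"). It separately lists tingling (75%), itching (30%), fatigue (35%) and headache (11.8%) from a cited tDCS safety study, adding that most of these did not differ from placebo stimulation. Participants are asked to report discomfort as soon as it occurs. The Data analysis table has only the SST and the DDT as dependent variables; no side effect summary is specified.

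**The concern.** Two of the four listed tDCS effects, fatigue and headache, are also plausible results of a long visit with interviews, an EEG cap and computer tasks, and much of that burden falls before stimulation. A form given only afterwards records a symptom without showing whether it was already there. The measure intended to detect adverse events of stimulation is thus the one repeated-task-day measure without a baseline.

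The second issue is position. The plan uses the word session for the 20-minute application, which suggests that the form comes directly afterwards; but the sentence stands after the one on post-stimulation resting EEG, which suggests the end of the visit. On the first reading the form precedes the post-stimulation tasks, and hence most of the approximately one hour for which the plan expects an effect to last. Symptoms starting later would then rely on spontaneous report. Questions about sensations would also come just before the outcome tasks, in a trial whose participant blinding depends on sham feeling like active stimulation.

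At stake is how interpretable the safety data are in an age group in which, by the protocol's own account, tDCS has been less studied.

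**Working it through.** The plan states no sample size, power or precision for side effects, so there is no figure to reproduce. The check asks what the sham contrast can show and what a pre-stimulation rating would add.

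**Inputs.** From the document: 20 per arm, so 20 v 20 for one active arm against sham, or 40 v 20 with both active arms pooled; 35% (fatigue) and 11.8% (headache) from the safety study cited under Potential Risk. Those rates are not predictions for this trial and serve only as illustration. Assumed: two-sided 5% level, 80% power, and a pre-post correlation ρ of symptom severity from 0.3 to 0.9, since the document gives none.

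**1. Expected counts at those rates.** Pooled active arms: 40 × 0.35 = 14 with fatigue and 40 × 0.118 = 4.7 with headache. Sham: 20 × 0.35 = 7 and 20 × 0.118 = 2.4.

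**2. Precision of active minus sham if the true rates are equal.** Half-width = 1.96 × √[p(1 − p)(1/n₁ + 1/n₂)].

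- Fatigue, 40 v 20: 1.96 × √(0.35 × 0.65 × 0.075) = 0.256
- Headache, 40 v 20: 1.96 × √(0.118 × 0.882 × 0.075) = 0.173
- Fatigue, 20 v 20: 1.96 × √(0.35 × 0.65 × 0.10) = 0.296
- Headache, 20 v 20: 1.96 × √(0.118 × 0.882 × 0.10) = 0.200

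With so few headaches the normal approximation is rough, but the order of size is clear.

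**3. Active-arm rate detectable with 80% power.** Power = Φ[(|p₁ − p₀| − 1.96·SE₀)/SE₁], with SE₀ from the pooled rate and SE₁ from the separate rates; solved for p₁.

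| Sham rate assumed | 20 v 20 | 40 v 20 |
|---|---|---|
| Headache 11.8% | about 52% | about 46% |
| Fatigue 35% | about 78% | about 72% |

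**4. Gain from a pre-stimulation rating, for a severity score at 20 v 20.** Minimal detectable difference in SD units, with the rating as a covariate: (1.960 + 0.842) × √[(1/20 + 1/20)(1 − ρ²)].

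| ρ (assumed) | Detectable d |
|---|---|
| no pre-rating | 0.89 |
| 0.3 | 0.85 |
| 0.5 | 0.77 |
| 0.7 | 0.63 |
| 0.9 | 0.39 |

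If the factor √(1 − ρ²) is carried over loosely to step 2 for ρ = 0.5 to 0.7, the 40 v 20 half-widths fall from 26 to 22–18 points (fatigue) and from 17 to 15–12 points (headache). The factor belongs to a continuous score, so this is only a guide.

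**5. Late onset, only if the form is given straight after stimulation.** If 10% to 50% of headaches began after the form (an assumption without a source in the document), 4.7 × 0.1 = 0.5 to 4.7 × 0.5 = 2.4 of the expected 4.7 would not be recorded on it.

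**The case against.** The strongest reply is the sham arm. A reader might infer from the missing baseline that battery effects and tDCS effects cannot be separated at all. The document does not support that. Allocation is randomised, the described battery is the same in every arm, and participants are masked: "As this commonly used sham procedure produces a brief tingling sensation, participants are kept unaware of their experimental condition". Active minus sham removes the battery's contribution on average without any pre-rating. This part of the objection stands in full; what remains is imprecision and weak attribution in individuals.

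A reader might also infer that tolerability is a main product of the trial. The overview states the aim as the short-term effect on impulsivity, and every row of the analysis table is SST or DDT. The form is a safety check.

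The points on late onset and on cueing depend on the form coming directly after stimulation, which is not stated. If it comes at the end of the visit, cueing disappears and late onset largely does. Nor can the items be seen, so the form may already ask about onset or relation to stimulation. Part of the text between Protection against Risk and the references was not in the copy reviewed, so a later check described there cannot be ruled out. Immediate reporting of discomfort is partial cover, but it is unstructured.

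Finally, a pre-rating does not cure the imprecision: step 4 leaves wide intervals. It could also prompt participants to notice whether tingling persists, and the sham current returns to zero after a short ramp. That is a real, small cost.

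**Conclusion.** The point holds as a low-severity, inexpensive improvement. The available text describes a post-stimulation form only, so an individual's fatigue or headache cannot be classed as new since stimulation unless the unseen items happen to ask about onset. The sham comparison is unbiased for the group question but imprecise: about ±26 points for fatigue and ±17 for headache at 40 v 20, and ±30 and ±20 at 20 v 20, taking the cited rates as equal in both groups. Missed later symptoms and attention to sensations before the outcome tasks are conditional concerns, valid only if the form precedes those tasks. The main gains from a pre-rating are attribution in individuals and, depending on an unknown correlation, some precision.

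**What to change.** Give the same form twice: once before stimulation, and once after the post-stimulation tasks and resting EEG, worded to cover the whole period since stimulation began. State both positions in the stimulation-session paragraph. Keep the immediate reporting of discomfort under Potential Risk as it is.

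Add a line to Data analysis: new or worsened symptoms, relative to the pre-stimulation rating, will be reported by arm, with differences from sham and 95% intervals, as a descriptive safety summary. If severity is scored, use the pre-rating as a covariate instead of subtracting it; for ρ below 0.5 a change score is less precise than the post-stimulation score alone (at ρ = 0.3, detectable d of 1.05 against 0.89).

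The cost is one more short form per participant and a few sentences of text. The downside is possible mild priming of symptom reporting, including attention to whether tingling continues. Placing the second form after the outcome tasks keeps that form from influencing them; the first form's effect cannot be excluded and should be acknowledged.

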Two Choice Impulsivity Paradigm (TCIP; Dougherty et al., 2003): The TCIP will be used as a delay discounting task (DDT) to assess impulsive choice, which requires participants to choose between immediate but small rewards and delayed but larger rewards over 50 trials. Delay discounting (or impulsive choice), is the tendency to undervalue an anticipated future reward as the time delay to obtaining the reward increases. A higher discounting rate (i.e., preference for smaller immediate rewards over larger delayed rewards) is viewed as reflecting greater cognitive impulsivity.

Stop-Signal Task (SST; Hamilton et al., 2015): The SST will be used to assess behavioral impulsivity. The SST requires participants to respond to a target stimulus as quickly and accurately as possible by pressing a button, but also to withhold their response when they hear an auditory signal. Thus, this task involves a competition between activating and inhibiting processes.

iv. **tDCS and EEG.** tDCS will be applied and EEG recordings made using a starstim/enobio device, with stimulation and recording electrodes located inside the cap. This device provides the user with up to 8 stimulating electrodes that can be programmed through software to be either anodal or cathodal in polarity and up to 32 recording electrodes. When not being used for stimulation, the 8 stimulating electrodes can also be used for recording, allowing for a total of 40 electrodes to be used for recording EEG pre- and post-stimulation. As in past studies, electrodes will be placed according to standard 10-10 coordinates corresponding to the rIFG (anode over F8 and cathode over FP1), which has been associated with behavioral impulsivity, and the IOFC (anode over FP1 and cathode over FP2), which has been linked with cognitive impulsivity.

Data analysis

Aim	Hypothesis	Dependent	Independent†	Analysis	MDE‡
1	H1	SST	tDCS/rIFG, time, tDCS/rIFG×time	GLM (repeated-measures ANOVA)	d=0.35
2	H2	SST	As above, plus reduced theta power (EEG), increased P3 (ERP)	As above with effects for EEG and ERP added; change in tDCS parameter estimate informs mediation	r=0.35
EA	EH1	DDT	tDCS/IOFC, time, tDCS/IOFC×time	GLM (repeated-measures ANOVA)	d=0.35
	EH2	DDT	As above, plus reduced VLFO (EEG), reduced SCPs (ERP)	As above with effects for EEG and ERP added; change in tDCS	r=0.35

† All analyses will include PROMIS (depressive symptoms) and Connor-3 (ADHD symptoms) as covariates

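### Task order is counterbalanced but absent from all four models, and balance within arm is not stated: a small loss of precision, not a bias

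*Combined protocol and SAP*

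**What the plan says.** All references are to the combined protocol and SAP.

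- **Tasks and timing.** The procedures text following Consenting and Screening Evaluation says that before stimulation "participants will complete the SST and TCIP, while EEG is recorded to extract ERPs in a single-blind procedure". The opening study description adds: "Baseline impulsivity measures will be re-given after tDCS or sham stimulation to assess changes in impulsivity". Pre/post change is therefore the outcome.
- **Order.** The same procedures text states: "Ordering of tasks will be counterbalanced". It does not say whether this is done within arm, or whether a participant has the same order before and after stimulation.
- **Effect window.** The tasks are said to fit comfortably inside an hour, described as "the approximate duration of effect from a single-session of tDCS".
- **Models.** The Data analysis table lists "tDCS/rIFG, time, tDCS/rIFG×time" for H1 and "tDCS/IOFC, time, tDCS/IOFC×time" for EH1. H2 and EH2 add EEG and ERP terms. The footnote adds: "All analyses will include PROMIS (depressive symptoms) and Connor-3 (ADHD symptoms) as covariates". None of the four models has an order or order×time term.

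**The concern.** A factor built into the design would normally be carried into the analysis. There are two tasks and so two orders, and the task done second comes later in a session of about 3.5 hours. The Potential Risk section itself expects that participants may become bored or tired. If order affects the amount of pre/post change, that variation has to go somewhere when the model has no order×time term.

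The plan's assumed correlation of 0.9 makes the variance of change small, so a given order effect would be a larger share of it than in a noisier design. What is at stake is some power and the calibration of the standard error in a trial with 20 per arm. The direction of the estimate is not at stake.

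**Working it through.** **Inputs from the documents.** 20 per arm and N=60 (opening description); correlation 0.9, type I error 5% and type II error 20% (Data analysis footnote); stated detectable effect d=0.35 (table). Two-sided testing is assumed because sidedness is not stated.

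**Input not in the documents.** The order effect b, meaning the difference in mean change between the two orders in outcome SDs. It is taken as 0 to 0.4.

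**1. The plan's own figure.** Variance of change = 2(1−0.9) = 0.20, so SD = 0.447. Detectable effect = (1.96+0.84) × 0.447 × √(1/n₁+1/n₂).
- 20 v 40 (one active arm against the other two pooled): 0.343, or 0.349 with the t distribution. This matches d=0.35.
- 20 v 20 (one active arm against sham): 0.396, or 0.407 with the t distribution. One-sided, 20 v 20 gives 0.352, so the stated figure does not settle which contrast was meant.

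The 20 v 20 calculations below use d=0.41, where power is about 80%.

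**2. Variance added by a common order effect.** A two-level, equally split factor adds b²/4 to the variance of change.

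| b | b²/4 | as share of 0.20 |
|---|---|---|
| 0.2 | 0.0100 | 5% |
| 0.3 | 0.0225 | 11% |
| 0.4 | 0.0400 | 20% |

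**3. Order not balanced within arm.** The difference between two arms of 20 in the share having a given order has SD √(2×0.25/20) = 0.158. At b=0.3 the arm contrast therefore moves by chance with SD 0.158×0.3 = 0.047. The contrast variance without order is 0.20×2/20 = 0.020, and the imbalance adds (0.158×0.3)² = 0.00225, which is 11%. This is the same 11% as in step 2, now in the contrast. Type I error stays near 5%.

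**4. Order balanced within arm.** There is no imbalance, but the order variance stays in the residual, so the standard error is too large by a factor √(1+b²/0.80) = 1.025, 1.055, 1.095 for b = 0.2, 0.3, 0.4. Applied to the two-sided critical value t₃₈ = 2.024, this gives type I error of about 4.5%, 3.9% and 3.3%. Simulations gave about 3% to 4.6% over this range, and about 5% with order in the model.

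**5. Power with and without the term.** Simulated, 20 v 20, d=0.41:

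| b | order independent of arm: without v with | gain (points) |
|---|---|---|
| 0 | 80 v 79% | −1 |
| 0.2 | 78 v 79% | +1 |
| 0.3 | 76 v 79% | +3 |
| 0.4 | 73 v 79% | +6 |

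With order balanced within arm, power without the term is about 79%, 77% and 75% for b = 0.2, 0.3, 0.4, against 80–81% with it. At b=0 the two are equal (about 81%). For 20 v 40 at the plan's d=0.35, omitting order takes power from 81.5% to 79.6%, 77.3% and 74.2%.

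**6. Order acting only in the active arm (waning).** In the setting of step 5 with order independent of arm, power without v with the term is 79.7 v 79.0% (0.2), 78.6 v 78.7% (0.3) and 77.3 v 78.5% (0.4), a gain of about −1 to +1 point.

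**7. Which term matters.** An order main effect enters only the between-subject stratum and leaves the error for arm×time unchanged. Order×time is the useful term. If each participant keeps one order, a constant position effect cancels in the change. If the order switches, it enters the change directly.

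**The case against.** The case against making much of this is strong, and most of it stands.

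- **The size is wholly assumed.** On a change SD of 0.447, order effects of 0.2, 0.3 and 0.4 SD are 0.45, 0.67 and 0.89 change-SDs. The largest exceeds the plan's detectable treatment effect of 0.35. At 0.2 the gain is about 1 point.
- **Waning is a weak argument.** A reader might infer from the one-hour window that the second task is measured as stimulation fades, and that this drives the loss. The plan answers part of this by choosing tasks that fit inside the window. Waning can also occur only under active stimulation, which makes it an order×arm×time effect that order×time barely recovers (step 6).
- **Fatigue may cancel.** With the same order before and after stimulation, only an order effect that differs between the two sittings remains. The documents do not say which applies.
- **There are not two harms.** A reader might add the lost power to the chance imbalance. Steps 3 and 4 show that they are alternatives: the same variance appears either in the contrast or in the residual.
- **The 0.9 may already include order variance.** Planned power would then not be lowered, and the term would be a bonus: the 20 v 40 detectable effect would fall from 0.343 to 0.334, 0.323 or 0.307 for b = 0.2, 0.3, 0.4.

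What survives is that the factor is in the design, is missing from all four models, and has no stated relation to arm. Being counterbalanced does not by itself settle the matter: without balance within arm the contrast picks up extra noise, and with it the unadjusted test is conservative.

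**Conclusion.** The omission is real and the consequence is minor. A reader might infer that leaving order out biases the stimulation effect or invalidates the test. The documents do not support that: arms are randomized, so the unadjusted arm×time estimate is unbiased on average, and type I error is at or below about 5% in either case.

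The benefit of adding the term runs from about −1 to +6 power points for common order effects on change of 0 to 0.4 SD (20 v 20, d=0.41, order independent of arm). It is near zero under active-arm waning or if the effect cancels. These figures rest on the plan's correlation of 0.9 being net of order, on two-sided 5% testing, and on an order effect that the documents do not give. This is an optional improvement in precision, worth making because it is nearly free.

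**What to change.** 1. Cross task order with the allocation list so that each arm of 20 has 10 participants in each order, and say so in the procedures text.
2. State that each participant keeps the same order before and after stimulation, so that a constant position effect cancels in the change.
3. Record the order used.
4. Add order and order×time to the H1, H2, EH1 and EH2 models in the Data analysis table, or order as a covariate if change or ANCOVA is used instead. Order×time is the term that does the work.

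The cost is 1 df in the test of interest, one more column in the allocation list, and no new data. If there is no order effect, the loss is at most about 1 power point, and essentially none once order is balanced within arm.
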